1.3. Schedule of Activities (SoA)

Status: Approved, Date: 21 July 2021

1.3.1. Groups 1 to 6 (56-day interval schedule [2-dose and single dose regimens]) – Adults\$

Phase	Screeninga		Study Period													
Clinic Visit #	1	2	3	4	5	6	7	8	9	10	11	12	UB**	13	14	Exit ^b
Visit Timing		Vac 1	Vac 1 + 7 d	Vac 1 + 14 d	Vac 1 + 28 d	Vac 2	Vac 2 + 7 d	Vac 2 + 14 d	Vac 2 + 28 d	Vac 2 + 4 mo	Inj 3 + 7 d	Inj 3 + 28 d		Inj 3 + 6 mo	Vac 2 + 12 mo	
Visit Day ±Window	-28 to 1	1	8±2°	15±3	29±3	57 -3/+7	64*±2°	71*±3	85*±3	169*±14	176*±2°	197*±3		337*±21	393*±21	
Visit Type	Screening	Vaccine 1	Safety		Safety and Immuno	Vaccine 2		Safety and Immuno		Antigen presentation or Placebo Injection 3 ^d	1.1	Safety and Immuno	Unblind to primary vaccination regimen ^t	Safety Phone Call	Safety and Immuno	Early Exit
Written informed consente	•												•			
Inclusion/exclusion criteria	•	•1														
Demographics	•															
Medical history/prestudy meds	•															
Physical examination ^f	•															
Pulse oximetry		●1														
Distribution of pulse oximeter ^g		•														
Vital signs ^h incl. body temperature	•	●2	•	•	•	● ²	•	•	•	●2	•	•			•	●4
Nasal swab sample and test for SARS CoV 2 RNA	●6	●7														
Serological test for anti SARS CoV 2 antibody	●6 8	• ⁷ (8)														
Randomization		●1														
Unblinding													•			
Prevaccination check ⁱ		●1				●1				●1						
Urine pregnancy test	•	●1				●1				●1						
Hematology blood sample plasma, mL ^v						● ¹ 5	●5	●5	●5						●5	
Hematology blood sample serum ^u		□8		□8	□8	□8	□8	□8	□8	□8	□8	□8			□8	

Phase	Screening ^a		Study Period													
Clinic Visit #	1	2	3	4	5	6	7	8	9	10	11	12	UB**	13	14	Exit ^b
Visit Timing		Vac 1	Vac 1 + 7 d	Vac 1 + 14 d	Vac 1 + 28 d	Vac 2	Vac 2 + 7 d	Vac 2 + 14 d	Vac 2 + 28 d	Vac 2 + 4 mo	Inj 3 + 7 d	Inj 3 + 28 d		Inj 3 + 6 mo	Vac 2 + 12 mo	
Visit Day ±Window	-28 to 1	1	8±2°	15±3	29±3	57 -3/+7	64*±2°	71*±3	85*±3	169*±14	176*±2°	197*±3		337*±21	393*±21	
Humoral immunity (serum), blood draw, mL		●¹ 15		• 10	• 10	●¹ 10	• 10	• 10	• 10	●¹ 10	• 10	• 15			• 15	● ³ 10
Cellular immunity (PBMC), blood draw, mL ^k		●¹ 60			• 60				● 60			● 60			● 60	● ³ 60
Cellular immunity (whole blood, PAXgene® tubes), mL		●¹ 2.5														
Vaccination		•				•				•						
1 hour post vaccination observation ¹		•				•				•						
Solicited AE recording		- Conti	- Continuous - Continuous-													

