1.3.2. Groups 7 and 8 (28-day interval schedule)- Adults\$

Phase	Screening ^a		Study Period												
Clinic Visit #	1	2	3	4	5	6	7	8	9	10	UB**	11	12	Exitb	
Visit Timing		Vac 1	Vac 1 + 7 d	Vac 2	Vac 2 + 7 d	Vac 2 + 14 d	Vac 2 + 28 d	Vac 2 + 4 mo	Inj 3 + 7 d	Inj 3 + 28 d		Inj 3 + 6 mo	Vac 2 + 12 mo		
Visit Day ±Window	-28 to 1	1	8±2°	29±3	36*±2°	43*±3	57*±3	141* ±14	148*±2°	169*±3		309*±21	365*±21		
Visit Type	Screening	Vaccine 1	Safety	Vaccine 2		Safety and Immuno		Antigen presentation or Placebo Injection 3 ^d	Safety and Immuno	Safety and Immuno	Unblind to primary vaccination regimen ⁸	Safety Phone Call	Safety and Immuno	Early Exit	
Written informed consent ^e	•										•				
Inclusion/exclusion criteria	•	●1													
Demographics	•														
Medical history/prestudy meds	•														
Physical examination ^f	•														
Pulse oximetry		●1													
Distribution of pulse oximeter ^g		•													
Vital signsh incl. body temperature	•	● ²	•	● ²	•	•	•	● ²	•	•			•	●4	
Nasal swab sample	●6	●7													
Serological test for anti SARS CoV 2 antibody	●6 8	● ⁷ (8)													
Randomization		●1													
Unblinding											•				
Prevaccination checki		● ¹		●1				●1							
Urine pregnancy test ^j	•	●1		●1				●1							
Hematology blood sample, plasma, mL ^u				● ¹ (5)	●5	●5	●5						●5		
Hematology blood sample, serum ^t		□8		□8	□8	□8	□8	□8	□8	□8	 		□8	- 3	
Humoral immunity (serum), blood draw, mL		●¹ 15		●¹ 10	● 10	• 10	● 10	●1 10	• 10	• 15			• 15	● ³ 10	
Cellular immunity (whole blood, PAXgene® tubes), mL		●¹ 2.5													
Vaccination		•		•				•							
1 hour post vaccination observation ^k		•		•				•							
Solicited AE recording		- Continuous Continuous Continuous										●4			
Unsolicited AE recording		-Conti	inuous ı +28 d-		Continuous	through +28	8 d	Conti	nuous throug	gh +28 d-				●5	
SAE/AESI recording ^m							C	ontinuous						•	

Phase	Screening ^a							Study Perio	od						
Clinic Visit #	1	2	3	4	5	6	7	8	9	10	UB**	11	12	Exitb	
Visit Timing		Vac 1	Vac 1 + 7 d	Vac 2	Vac 2 + 7 d	Vac 2 + 14 d	Vac 2 + 28 d	Vac 2 + 4 mo	Inj 3 + 7 d	Inj 3 + 28 d		Inj 3 + 6 mo	Vac 2 + 12 mo		
Visit Day ±Window	-28 to 1	1	8±2°	29±3	36*±2°	43*±3	57*±3	141* ±14	148*±2°	169*±3		309*±21	365*±21		
Concomitant meds ⁿ															
Participant diary distribution ^o		•		•				•							
Participant diary review ^p			•		•				•						
COVID 19 like Symptom surveillance booklet and nasal swab kit training and distribution		•													

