8.2.4. Hematology Clinical Laboratory Assessments

Blood samples for hematology (as detailed in Section 10.2) to evaluate D-dimers and Lupus anticoagulant, anti- β 2 glycoprotein, anti-cardiolipin (adults) and anti-PF4 (adults and adolescents) will be collected at the timepoints indicated in the Schedules of Activities (see Section 1.3). For timepoints that have already passed before protocol Amendment 2 was approved and implemented, the D-dimers, Lupus anticoagulant, and anti-PF4 tests will not be performed retrospectively, as these tests are to be performed in plasma samples. Serum samples originally drawn or yet to be drawn for the humoral immunogenicity assessments will be used for the testing of Anti- β 2 glycoprotein, anti-PF4 and anti-cardiolipin. Collection of plasma and serum samples for testing of D-dimers, Lupus anticoagulant, Anti- β 2 glycoprotein, anti-PF4, and Anti-cardiolipin will be performed for all groups from the time of approval of Amendment 3.

The investigator must review the laboratory results, document this review, and record any clinically relevant changes occurring during the study in the AE or medical history section of the case report form (CRF), as applicable.

In case of a thrombotic event or TTS, every effort should be made to collect local hospital/laboratory test results obtained by the treating physician to allow rapid diagnosis and treatment. This information should be reported through the TTS AESI form (see Section 10.13, Appendix 13) electronically per instructions in the eCRF completion guidelines. In addition, every

effort should be made to collect blood samples from the participant for a platelet count (local laboratory or substitute for local laboratory) and other applicable testing (central laboratory) (see the Schedule of Activities in Section 1.3.8 and Section 10.2, Appendix 2). The Investigator will review the laboratory test results to assist the investigation of the AESI.

See Section 8.3.6.1 for details on laboratory test details to be reported for an AE of thrombocytopenia.

8.3. Adverse Events, Serious Adverse Events, Adverse Events of Special Interest, and Other Safety Reporting

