1. INTRODUCTION

This SAP describes the pre-planned analyses for the Interim Analyses, Primary Analyses and Final Analysis, for all groups in the study. One or several Data Presentation Specification Documents will be available to further detail the statistical outputs that will be generated.

For some analyses (e.g. RNA sequencing data), a separate SAP may be written.

Due to the reactogenicity observed at the 2.5×10^{10} vp dose level, it was decided not to proceed to the 5×10^{10} vp dose level in adolescents.

Safety, reactogenicity and immunogenicity data will be summarized for the 33 enrolled adolescent participants. Only limited outputs will be provided.

The term “study vaccine” throughout the SAP, refers to Ad26.COV2.S or placebo as defined in Clinical Trial Protocol Section 6.1, Study Vaccinations Administered. Scientifically, the administration of the Ad26.COV2.S 1.25×10^{10} virus particles (vp) or placebo dose 4 months after the primary vaccination regimen in adults is considered as presentation of antigen. Nevertheless, for the sake of simplicity, the terms “study vaccine” and “vaccination” throughout the SAP encompass administration of the antigen presentation dose.

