5. STATISTICAL ANALYSES

5.1. General Considerations

5.1.1. Study phases

A baseline (or reference) value will be defined as the value of the last available assessment prior to the first vaccination on Day 1.

The safety analysis will present all results by phase (cf. section 5.1.2 for phase definitions). Immunogenicity results will be presented per scheduled time point as appropriate. Listings will be shown per phase and time point.

Study day or relative day is defined as follows:

Study Day = visit date - date of Day 1 + 1; if visit date \geq date of Day 1 (date of first vaccination).

Study Day = visit date - date of Day 1; if visit date $<$ date of Day 1 (date of first vaccination).

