5.6.2. Laboratory, Vital Signs and Physical Examination

Laboratory safety parameters, change from baseline and change from pre-dose x over time will be tabulated. Abnormalities on the changes from reference, if available, will be categorized. Abnormalities will be tabulated by visit and by worst abnormality. Patient profiles will be provided.

A listing of all laboratory values will be made, restricted to participants with at least one laboratory abnormality.

Physical examination findings will be summarized at baseline. A listing of the abnormalities will be made.

Vital signs including temperature, pulse/heart rate, respiratory rate, and blood pressure (systolic and diastolic) will be summarized over time, using descriptive statistics. Abnormalities emerging after vaccination will be tabulated by worst abnormality grade using the FDA table in appendix 3.

An abnormality (toxicity grade or abnormality based on normal ranges) will be considered as emerging in a particular period if it is worse than the baseline value. If the baseline is missing, the abnormality is always considered emerging. A shift from ‘abnormally low’ at baseline to ‘abnormally high’ post baseline (or vice versa) is also emerging. In case a laboratory test result is censored (no numeric value is available, but only a verbatim term) then a numeric value will be imputed by a value exceeding the cut-off value with one unit. (<x: subtract 1 unit from x, >x: add 1 unit to x; <3.45 is imputed with 3.44).

In case no toxicity grades are defined for a test, the abnormalities (above/below normal range) will be used. In determining toxicity grades, the following rules are applied:

- worst grades/abnormalities are determined over the whole observational period for each trial period separately, including all post-baseline measurements of that period.
- The abnormalities ‘abnormally low’ and ‘abnormally high’ are considered equally important, i.e. if a participant has as well an abnormally low as an abnormally high value post-baseline, both abnormalities are shown in the tables. (This means that the sum of the percentages can be more than 100%)
- Note: as the grading scale for some parameters in the grading table has some gaps (zones where no toxicity grade definition exists), laboratory results falling in these zones will be allocated to the adjacent worst-case grade.

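### No plasma is scheduled before Day 1, so the SAP's missing-baseline rule flags every routine abnormal D-dimer or lupus anticoagulant result as emerging, in active and placebo arms alike

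*SAP*

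**What the plan says.** **Emergence rule.** SAP 5.6.2 compares each abnormality with baseline and adds: "If the baseline is missing, the abnormality is always considered emerging". The rule covers graded results and results judged against normal ranges. D-dimer and lupus anticoagulant have no grade in SAP Appendix 3, so normal ranges apply.

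**Baseline.** SAP 5.1.1: "A baseline (or reference) value will be defined as the value of the last available assessment prior to the first vaccination on Day 1". The SAP Introduction says that study vaccine "refers to Ad26.COV2.S or placebo as defined in Clinical Trial Protocol Section 6.1", so a placebo injection on Day 1 also counts as the first vaccination.

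**Plasma schedule.** In protocol 1.3.1 to 1.3.3 the plasma row ("Hematology blood sample plasma, mL" for Groups 1-6, "Hematology blood sample, plasma, mL" for Groups 7-8, and its counterpart for Groups 9-10) is first marked at the second vaccination: Visit 6, Visit 4 and Visit 5 respectively. Nothing is marked at screening or on Day 1. Protocol 1.3.4 schedules pre-vaccination plasma at Visit 101, before the first active dose in Groups 6, 8 and 10.

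**Retrospective testing.** Protocol 8.2.4 says that for timepoints already passed, "the D-dimers, Lupus anticoagulant, and anti-PF4 tests will not be performed retrospectively, as these tests are to be performed in plasma samples". Protocol Appendix 2 allows a stored pre-vaccination sample to be tested after a suspected AESI.

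**The concern.** Counting a missing baseline as emerging is a reasonable cautious default when gaps are sporadic. Here the gap is built into the schedule and applies to everyone. A participant whose D-dimer was raised before any injection is then reported in the same way as one whose D-dimer rose afterwards.

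The two tests serve an exploratory objective on hematology parameters after vaccination, in a programme where thrombosis with thrombocytopenia is an identified risk. A reader of the tables will take 'emerging' to mean new since vaccination. After dose 1 the data cannot support that meaning.

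**Working it through.** **1. Is there a plasma tube before the Day 1 injection?** The stated blood volumes (protocol 1.3) answer this.
- Screening: 8 mL stated; the serological test alone is 8 mL.
- Day 1, Groups 1-6, outside the PBMC subset: serum 15 + PAXgene 2.5 = 17.5 mL; stated 17.5. A 5 mL plasma tube would give 22.5.
- Day 1, PBMC subset: 60 + 15 + 2.5 = 77.5 mL; stated 77.5.
- Second vaccination visit, all three schedules: serum 10 + plasma 5 = 15 mL; stated 15.
- Visit 101: serum 15 + PAXgene 2.5 + plasma 5 = 22.5 mL; stated 22.5.

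The volumes reproduce only with no plasma on Day 1, and with plasma at the second vaccination and at Visit 101.

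**2. Who has a reference value by schedule?** The active groups number 5 × 75 + 2 × 50 = 475 and the placebo groups 3 × 25 = 75, in total 550.
- Plasma before the SAP baseline cut-off (Day 1): 0 of 550.
- Plasma before the first active dose: 0 of 475 in the active groups, and up to 75 of 550 (13.6%) overall, from Visit 101. The SAP does not re-baseline to that sample.

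**3. What does the rule do to the rates?** Let p be the share already abnormal before Day 1 who stay abnormal, and d the true rate of new abnormality among the rest. SAP 5.6 takes all participants in the phase as denominator.
- Correct emerging rate: (1 − p)d.
- Flagged emerging rate: p + (1 − p)d.
- Excess: p, in every arm.
- Active minus placebo: (1 − p)(d_active − d_placebo) under either definition, if randomization balances p.

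So each arm's absolute rate rises by p. The expected risk difference survives, while the ratio is pulled towards 1.

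**4. Size, under an assumption.** The documents give no value for p. Taking 5% to 30% with complete sampling:
- Group of 75: 75 × 0.05 = 3.75 to 75 × 0.30 = 22.5 flagged without being new.
- Group of 50: 2.5 to 15.
- Group of 25: 1.25 to 7.5.

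**5. Which tests?** Anti-β2 glycoprotein, anti-cardiolipin and anti-PF4 can be run on serum, and serum is drawn on Day 1. The point is therefore confined to D-dimer and lupus anticoagulant.

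**The case against.** A reader might infer that the tables cannot show a signal at all. The documents do not support that. Placebo arms are randomized concurrently and flagged by the same rule, so an excess over placebo stays visible. SAP 5.6.2 also tabulates change from pre-dose values and abnormalities by visit, and provides patient profiles and listings. Its laboratory paragraph does not explicitly promise an emerging-only table; that commitment is worded for vital signs. The definition of emerging is nevertheless general and covers laboratory results.

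A reader might also infer that no pre-vaccination plasma exists for anyone, or that the SAP calls these events vaccine-emergent. Visit 101 contradicts the first. The SAP's word is emerging, and it applies after placebo too.

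The rule errs towards over-reporting, which can be defended for safety data. The endpoints are exploratory, no hypothesis is tested, and thrombotic events are handled separately through suspected-AESI reporting and adjudication. Pre-dose samples fall outside the post-dose period that follows them, because periods start at the time of injection.

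The strongest counterpoint concerns the remedy. Making the pre-dose 2 sample the sole reference would hide a lasting effect of dose 1. This is worst in Groups 4-5, whose only active primary dose is on Day 1 and whose second injection is placebo. That stands, and it shapes the fix. What the objections do not rescue is the label: a flag set for every abnormal routine result carries no information beyond 'abnormal'.

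**Conclusion.** The point holds for D-dimer and lupus anticoagulant in all ten adult groups. By schedule, 0 of 550 adults have a baseline as the SAP defines it, so 'emerging' and 'abnormal' coincide for routine results, and absolute emerging rates are too high by the share already abnormal before Day 1. The comparison with placebo and the other planned displays remain usable.

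This rests on the following:
- The documents show what was scheduled, not what was drawn.
- 550 is a ceiling. Plasma collection began mid-study, and the schedule footnotes (up to Amendment 2) conflict with protocol 8.2.4 (from approval of Amendment 3). These need reconciling, but neither adds Day 1 plasma.
- The counts in step 4 depend on an assumed 5% to 30% and are illustrative only.
- The suspected-AESI provision is a narrow exception. It is hard to square with 8.2.4, because the scheduled Day 1 tubes contain no plasma.
- It is unclear how far cross-vaccination periods will be tabulated: SAP section 4 censors safety analyses at unblinding, while SAP 5.1.2 defines those periods.

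**What to change.** In SAP 5.6.2:
1. Exempt D-dimer and lupus anticoagulant from the missing-baseline rule.
2. Tabulate their abnormalities by visit and arm under the label 'baseline not available', and state that emergence after dose 1 is not assessable.
3. For any cross-vaccination period that is tabulated in Groups 6, 8 and 10, use the pre-vaccination Visit 101 plasma as the reference.
4. For post-dose 2 periods, show shift from the pre-dose 2 sample only as an additional display labelled 'new since pre-dose 2'. Add a note that no shift does not mean no vaccine effect, because that sample follows dose 1 and dose 2 is placebo in Groups 4-5.

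The cost is a few lines of SAP text and minor programming, with no new data. The downside is that fewer events will be called emerging; the by-visit table keeps them in view.

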other groups, it might be possible to use the data according to that interval. In this case, further details will be provided in the SAP.

Table 4: Visit Windows Groups 1 to 6 (56-day interval schedule [2- and single-dose regimens]) – Adults

Visit	Visit Day	Allowed	Primary Purpose
		Window	
3ª	8	±2 days	7 days post-vaccination 1 safety visit
4	15	±3 days	14 days post-vaccination 1 safety and immunogenicity visit
5	29	±3 days	28 days post-vaccination 1 safety and immunogenicity visit
6	57	-3/+7 days	Vaccination 2
7ª	64 ^b	±2 days	7 days post-vaccination 2 safety and immunogenicity visit
8	71 ^b	±3 days	14 days post-vaccination 2 safety and immunogenicity visit
9	85 ^b	±3 days	28 days post-vaccination 2 safety and immunogenicity visit
10	169 ^b	±14 days	Antigen Presentation (Groups 1-5) or Placebo (Group 6)
11ª	176 ^b	±2 days	7 days post antigen presentation safety and immunogenicity visit
12	197 ^b	±3 days	28 days post antigen presentation safety and immunogenicity visit
UB			Unblinding to primary vaccination regimen*
13	337 ^b	±21 days	6 months post antigen presentation safety phone call
101	UB1		Unblinded vaccination 1
102	UB8°	±2 days	7 days post unblinded vaccination 1 safety and immunogenicity visit
103	UB29	-3/+7 days	Unblinded vaccination 2
104	UB36°	±2 days	7 days post unblinded vaccination 2 safety visit
105	UB43°	±3 days	14 days post unblinded vaccination 2 safety and immunogenicity visit
106	UB57°	±3 days	28 days post unblinded vaccination 2 safety and immunogenicity visit
107	UB169°	±21 days	6 months post unblinded vaccination 1 safety and immunogenicity visit
14	393 ^b	±21 days	12 months post-vaccination 2 safety and immunogenicity visit

Placebo Group 6 only

- a. If a participant comes in early for Visit 3, 7, or 11, ie, 1 or 2 days prior to the Visit Day per the allowed visit window, a subsequent phone call will be made at the end of the diary period to collect diary information recorded between the actual visit and the end of the diary period. The diary will then be returned by the participant at the next visit. If an event is still ongoing on the Visit Day, the participant should keep the diary after the review and collect information until resolution. The diary should be reviewed again at the next visit.
- b. The timings of visits after the second vaccination and antigen presentation will be determined relative to the actual day of that vaccination/antigen presentation.

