5.1.2. Phase definitions

The phases in the study will be constructed as detailed in [Table 1](#) and [Table 2](#).

Table 1: Phase Definitions for groups 1-10

Phase	Phase #	Period	Period #	Interval	
				From	To
Screening	1			Date and time of signing the informed consent form	One minute prior to start of post dose 1 period
Regimen	2	Post-dose 1	1	Date and time of first vaccination	Minimum of: a) 23:59 at the date of last contact (for early discontinuation) b) 23:59 at the date of database cut-off date in case of interim analysis c) 23:59 on 28 days after the first vaccination (23:59 of day of vaccination + 28 days) d) One minute prior to post-dose 2
Follow-up 1	3			One minute after Post dose 1 period end	Minimum of: a) 23:59 at the date of last contact (for early discontinuation) b) 23:59 at the date of database cut-off date in case of interim analysis c) One minute prior to post dose 2
Regimen	2	Post-dose 2	2	Date and time of second vaccination	Minimum of: a) 23:59 at the date of last contact (for early discontinuation) b) 23:59 at the date of database cut-off date in case of interim analysis c) 23:59 on 28 days after the second vaccination (23:59 of day of vaccination + 28 days)
Follow-up 2	4			One minute after Post-dose 2 period end	Minimum of:

					
 a) 23:59 at the Date of last contact (for early discontinuation) b) 23:59 at the date of database cut-off date in case of interim analysis c) One minute prior to Antigen presentation
Regimen	2	Antigen presentation or Placebo	3	Date and time of Antigen presentation or Placebo	Minimum of: 
 a) 23:59 at the date of last contact (for early discontinuation) b) 23:59 at the date of database cut-off date in case of interim analysis c) 23:59 on Day 28 after the Antigen presentation or Placebo (23:59 of day of Antigen presentation + 28 days)
Follow-up 3	5			One minute after Antigen presentation or Placebo period end	Minimum of: 
 a) 23:59 at the Date of last contact (for early discontinuation) b) 23:59 at the date of database cut-off date in case of interim analysis c) 23:59 at the Date of last visit d) One minute prior to post dose 4 period (groups 6, 8 and 10)

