6.2. Appendix 2 Changes to Protocol-Planned Analyses

In October 2020, the current study was temporarily paused because one of the pausing rules was met in study COV3001. When the pause was lifted, most of the participants in Groups 7-8 had missed their visit window for Vaccination 2, rendering the intent of the 28-day vaccination interval in these groups futile.

For safety analyses,

- the 2 subjects vaccinated before pausing rule (28-day interval) will only be shown in the listings.
- the other subjects received the vaccination 2 between 51 and 72 days after Vaccination 1. They will be integrated in the Full Analysis Set with groups 1 and 6 (56-day interval).

For immunogenicity analyses,

- subjects randomized in groups 7 and 8 won't be included in PPI set
- a modified PPI set will be defined as follows :
subjects with vaccination 2 within the window (54-64) or subjects who did not receive vaccination 2 will be integrated in groups 1 and 6
- a modified FAS set will be defined as follows :
subjects in mPPI set and subjects with vaccination 2 in (51-53) days or (65-72) days window

6.3. Appendix 3 Guidance for Industry: Toxicity Grading Scale for Healthy Adult and Adolescent Volunteers Enrolled in Preventive Vaccine Clinical Trials

The laboratory values provided in the tables below serve as guidelines and are dependent upon institutional normal parameters. Institutional normal reference ranges should be provided to demonstrate that they are appropriate.

If a laboratory value falls within the grading as specified below but also within the local laboratory normal limits, the value is considered as normal.

Serum *	Mild (Grade 1)	Moderate (Grade 2)	Severe (Grade 3)	Potentially Life Threatening (Grade 4)**
Sodium – Hyponatremia mEq/L	132 – 134	130 – 131	125 – 129	< 125
Sodium – Hypernatremia mEq/L	144 – 145	146 – 147	148 – 150	> 150
Potassium – Hyperkalemia mEq/L	5.1 – 5.2	5.3 – 5.4	5.5 – 5.6	> 5.6
Potassium – Hypokalemia mEq/L	3.5 – 3.6	3.3 – 3.4	3.1 – 3.2	< 3.1
Glucose – Hypoglycemia mg/dL	65 – 69	55 – 64	45 – 54	< 45
Glucose – Hyperglycemia Fasting – mg/dL Random – mg/dL	100 – 110 110 – 125	111 – 125 126 – 200	>125 >200	Insulin requirements or hyperosmolar coma
Blood Urea Nitrogen BUN mg/dL	23-26	27 – 31	> 31	Requires dialysis
Creatinine – mg/dL	1.5 – 1.7	1.8 – 2.0	2.1 – 2.5	> 2.5 or requires dialysis
Calcium – hypocalcemia mg/dL	8.0 – 8.4	7.5 – 7.9	7.0 – 7.4	< 7.0
Calcium – hypercalcemia mg/dL	10.5 – 11.0	11.1 – 11.5	11.6 – 12.0	> 12.0

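### Vital-sign abnormalities are tabulated only by worst grade per period, so merging the delayed Group 7-8 participants (two post-dose-1 clinic readings) into Groups 1 and 6 (four) lowers both merged columns against Groups 2-5

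*SAP*

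**What the plan says.** SAP 5.6.2 treats laboratory and vital-sign abnormalities differently. For laboratory data, "Abnormalities will be tabulated by visit and by worst abnormality". For vital signs, the values "will be summarized over time, using descriptive statistics", but the abnormalities get one display: "Abnormalities emerging after vaccination will be tabulated by worst abnormality grade using the FDA table in appendix 3". The rule for the worst grade is that "worst grades/abnormalities are determined over the whole observational period for each trial period separately, including all post-baseline measurements of that period". Under SAP 5.6 the denominator is participants in the population and phase, so nothing adjusts for how many readings each participant had.

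SAP 5.1.2, Table 1, ends the post-dose-1 period no later than "23:59 on 28 days after the first vaccination (23:59 of day of vaccination + 28 days"), which is Day 29.

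SAP Appendix 2 (6.2) deals with Groups 7 and 8, whose second vaccination was delayed by the October 2020 pause. For safety, the two participants vaccinated on schedule appear only in listings, while "the other subjects received the vaccination 2 between 51 and 72 days after Vaccination 1". Of these delayed participants it says: "They will be integrated in the Full Analysis Set with groups 1 and 6 (56-day interval").

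**The concern.** A worst grade is a maximum, and the chance that a maximum crosses a threshold rises with the number of readings behind it. If columns in one table rest on different numbers of readings, their rates differ even when the vaccine does nothing.

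That is the situation after dose 1. Groups 1-6 have a visit that Groups 7-8 and 9-10 lack, the "14 days post-vaccination 1 safety and immunogenicity visit" in Protocol Table 4, and a Day 29 visit that the delayed Group 7-8 participants also lack. Appendix 2 then puts those participants in the Group 1 and Group 6 columns, while Groups 2-5 stay undiluted.

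Two comparisons are at stake. Protocol 4.2 includes placebo to show how often changes occur without active vaccine; the merge lowers that reference against Groups 2-5. And Groups 1 and 5 received the same first dose, yet merged Group 1 would be expected to look milder.

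**Working it through.** **Check of the formula.** The plan gives no vital-sign rate to reproduce. The at-least-one formula 1 − (1 − p)^k is the one behind Protocol Table 10: with 25 participants and true rates of 0.5, 1, 2.5 and 10% it gives 11.8, 22.2, 46.9 and 92.8%, against the printed 12, 22, 47 and 93%.

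**Scheduled clinic readings in post-dose 1** (Protocol Schedules 1.3.1-1.3.3, cut at Day 29):

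| Groups | Readings | k |
|---|---|---|
| 1-6 | post-injection, Days 8, 15, 29 | 4 |
| 9-10 | post-injection, Days 8, 29 | 3 |
| 7-8, delayed | post-injection, Day 8 | 2 |

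For delayed Groups 7-8 the next scheduled visit is Vaccination 2. At 51-72 days, its pre-dose reading falls in Follow-up 1. Visit 5 of Groups 1-6 has a window of ±3 days, so an in-window visit on Days 30-32 also falls in Follow-up 1 and leaves k = 3.

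**Composition of the merged columns** (Protocol 4.1 target sizes, less one on-schedule participant each in Groups 7 and 8):
- Placebo: 25 from Group 6 and 24 from Group 8. Two-reading share 24/49 = 49%; mean readings (25×4 + 24×2)/49 = 3.02.
- Group 1: 75 from Group 1 and 49 from Group 7. Two-reading share 49/124 = 40%; mean readings (75×4 + 49×2)/124 = 3.21.
- Groups 2-5: four readings each.

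**Expected rates with no vaccine effect and independent readings.** The per-reading probability p of an emergent graded abnormality is not in the documents; 5, 10 and 20% are assumed. At p = 5%, four readings give 1 − 0.95⁴ = 18.5%, two give 1 − 0.95² = 9.8%, and merged placebo is (25×18.5 + 24×9.8)/49 = 14.2%.

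| | p = 5% | p = 10% | p = 20% |
|---|---|---|---|
| Groups 2-5 (k = 4) | 18.5% | 34.4% | 59.0% |
| Group 10 (k = 3) | 14.3% | 27.1% | 48.8% |
| Merged Group 1 | 15.1% | 28.3% | 49.9% |
| Merged placebo | 14.2% | 26.9% | 47.8% |
| Groups 2-5 minus merged placebo | 4.3 | 7.5 | 11.3 |
| Merged Group 1 minus merged placebo | 0.8 | 1.5 | 2.2 |

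(Differences, in points, come from unrounded rates.)

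**Sensitivity**, Groups 2-5 minus merged placebo, in points:

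| | p = 5% | p = 10% | p = 20% |
|---|---|---|---|
| Within-person correlation 0.3 | 2.2 | 3.9 | 6.3 |
| Within-person correlation 0.5 | 1.3 | 2.4 | 4.0 |
| k = 3 in Groups 1-6, independent | 2.2 | 4.0 | 6.3 |

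The correlated cases use a beta-binomial model. At correlation 0.5 the chance of no abnormality in k readings is the product over j = 0 to k − 1 of (1 − p + j)/(1 + j). At p = 5% this gives 7.4% abnormal with two readings and 10.1% with four. In every case run the sign is the same.

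**The case against.** The strongest reply is that this is a peripheral output. The primary safety endpoints are solicited and unsolicited AEs, SAEs and AESIs; SAP 5.6 plans no formal group comparison, and no test uses the table. Vital-sign values are already shown over time, and fever and temperature have their own outputs. A worst grade over all data is also a cautious safety convention. All of this stands. It limits the importance of the point but does not remove the artefact: side-by-side columns are how descriptive safety data are read, and no planned output grades vital-sign abnormalities by visit.

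Sampling noise is a fair point too. With 49 merged placebo participants, the 95% half-width at 14.2% is 1.96 × √(0.142 × 0.858/49), about 10 points, and about 12 and 14 points at 26.9% and 47.8%. The expected gap is smaller than that. It is nevertheless systematic and avoidable.

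A reader might infer more than the documents support:
- *That the merge penalises placebo alone and so manufactures a vaccine excess everywhere.* It dilutes Group 1 as well (40% against 49%), leaving little between those two columns.
- *That every period is affected between groups.* Post-dose 2 has four scheduled readings and antigen presentation three, in every group. The between-group imbalance is confined to post-dose 1 and any combined period containing it.
- *That fever is distorted in the same way.* Temperature is also recorded daily in the diary, on the vaccination day and the next seven days, in every group.
- *That unsolicited AEs are under-ascertained in delayed Groups 7-8.* They do lack the Day 15 and Day 29 visits, but recording runs continuously for 28 days and participants report throughout the study. The documents give nothing from which to establish or size a shortfall.

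**Conclusion.** The point holds as a limited one. Followed as written, the plan makes the merged placebo and merged Group 1 columns both expected to show lower post-dose-1 worst-grade rates of clinic-measured heart rate, blood pressure and respiratory rate than Groups 2-5, with no vaccine effect needed.

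The direction follows from the schedules and the merge rule, provided a Day 15 or Day 29 reading has some chance of showing an abnormality that the first two did not. The size rests on assumed per-reading rates, on the within-person correlation, on target group sizes, and on visits being on schedule with no extra readings during the pause. Rates of 5-20% are not far-fetched, since Appendix 3 of the SAP grades a respiratory rate of 17-20 as an abnormality, but they remain assumptions. The independent-reading figures are best read as the upper part of the range, because repeated readings in one person are usually correlated.

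**What to change.** In SAP 5.6.2, tabulate emergent vital-sign abnormalities by scheduled time point as well as by worst grade, as is already planned for laboratory data. At a given time point each participant contributes one scheduled reading, so the number of readings no longer drives the rate.

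In SAP Appendix 2, show the delayed Group 7-8 participants as separate columns in the post-dose-1 worst-grade vital-sign table, or add a sensitivity table without them. Footnote the number of scheduled readings behind each column.

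Keep the worst-grade table over all readings. Restricting it to the shared post-injection and +7-day readings would also equalise the columns, but would discard half of the four scheduled readings in Groups 1-6, which is hard to justify for safety data.

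The cost is SAP wording and a few extra descriptive tables. No new data are needed.
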